7.7. Patient-reported Outcomes (PROs)

Subjects will complete the PROs at the clinic prior to other clinical activities and investigational product administration. The PROs should be checked for completeness by the study site staff before proceeding with other steps of the clinical visit procedures. Compliance with scheduled PROs activities will be monitored. Delegated site staff will oversee the administration of PROs at site visits to ensure protocol compliance. Subjects are given a handheld device to complete the Pruritus NRS and PSAAD according to the [Schedule of Activities](#). Delegated site staff will review compliance at each visit and counsel as appropriate. If a subject has repeated non-compliance, the subject should be re-trained on the device. If a subject is unable to complete the PROs on the handheld device due to documented difficulty using the technological devices or other limitation, the subject will be permitted to enter or remain in the study. In the event of electronic malfunction, a replacement device will be shipped to the site.

Examples of the validated paper versions of Patient Reported Outcomes instruments are included in the Appendices of this protocol. In instances where an electronic device is used to collect the PRO data, the electronic version may differ slightly in format or wording compared with the paper version to facilitate electronic implementation.

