- q. Pruritus Numerical Rating Scale (NRS) will be assessed using an eDiary, daily during the screening period and from Day 1 to 15. After Day 15, the pruritus NRS will be completed only on study visit days in the eDiary. At the Screening visit, site staff will dispense the ePRO device and review instructions for completion of the subject eDiary for the NRS. At every visit, the study coordinator will review the eDiary for completeness and counsel the subject on how to complete the items in the daily eDiary, if needed.
- r. Pruritus and Symptoms Assessment for Atopic Dermatitis (PSAAD) will be conducted to assess the severity and frequency of pruritus, symptoms and sleep collected daily in a subject e-diary during the screening period and from Day 1 through the End of Study visit in selected countries (See [Section 7.7.7](#)). At the Screening visit, site staff will dispense the ePRO device and review instructions for completion of the subject eDiary for the PSAAD questionnaire. Subjects will be asked to record their assessment in their eDiary once a day before taking the investigational product. At every visit, the study coordinator will review the eDiary for completeness and counsel the subject on how to complete the items in the daily eDiary, if needed.
- s. The contraception check is an opportunity to confirm that contraception, if assigned, is used consistently and correctly. It also facilitates continual reassessment of child-bearing potential in women. This allows for implementing necessary changes to contraception; for example, investigators may need to ensure alternative contraceptive methods if new concomitant disease contraindicates a selected method of contraception, or if a subject is demonstrably no longer of child-bearing status (as per protocol) then they will no longer require contraception. Continual reassessment of contraceptive needs is imperative.
- t. SF-36v2 will be completed by adult subjects only. Adolescents 12-17 years of age will not complete this assessment.
- u. A serum sample will be collected at baseline but analyzed only if the subject has suspected varicella or herpes zoster. In that event, the sample would be analyzed for HSV1, HSV2 and VZV.
- v. Subjects who complete EOT will be assessed for eligibility for participation in long-term extension study B7451015 as noted in [Section 6.2.7](#).
- w. FACIT-F will be completed by adult subjects only. Adolescents 12-17 years of age will complete the Peds-FACIT-F instead.

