
Secondary Objective: To evaluate the effect of PF-04965842 on additional efficacy endpoints and patient reported outcomes over time in subjects aged 12 years and older with moderate to severe atopic dermatitis.
	
Secondary Endpoints:
 
Key Secondary Endpoints:
 
 • Response based on at least 4 points improvement in the severity of pruritus numerical rating scale (NRS) from baseline at Weeks 2, 4, and 12; • Change from Baseline in Pruritus and Symptoms Assessment for Atopic Dermatitis (PSAAD) total score at Week 12. 
Secondary Efficacy Endpoints:
 
 • Response based on at least 4 points improvement in the severity of pruritus numerical rating scale (NRS) from baseline at all scheduled time points other than Weeks 2, 4 and 12; • Time from baseline to achieve at least 4 points improvement in the severity of pruritus NRS scale; • Response based on the EASI-75 at all scheduled time points except Week 12; • Response based on the IGA of clear (0) or almost clear (1) and ≥ 2 point reduction from baseline at all scheduled time points except Week 12. 
Other Efficacy Endpoints:
 
 • Response based on a $\geq 50\%$ and $\geq 90\%$ improvement in the EASI total score (EASI-50 and EASI-90) at all scheduled time points; • Change from baseline in the percentage Body Surface Area (BSA) affected at all scheduled time points; • Response based on a $\geq 50\%$ and $\geq 75\%$ improvement in SCORAD (SCORAD50, SCORAD75) from baseline at all scheduled time points; • Change from baseline at all scheduled time points in SCORAD subjective assessments of itch and sleep loss. 
Patient-reported Outcomes:
 
 • Change from baseline at Week 12 in Dermatology Life Quality Index (DLQI) or Children’s DLQI (CDLQI) and at all other scheduled time points;

090177e1912f28afApproved\Approved On: 26-Jun-2019 09:23 (GMT)

Table 1. Objectives and Endpoints

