4.1. Inclusion Criteria

Subjects must meet all of the following inclusion criteria to be eligible for enrollment into the study:

1. Evidence of a personally signed and dated informed consent document indicating that the subject or their parent(s)/legal guardian, if applicable, have been informed of all pertinent aspects of the study.
2. Male or female subjects of 12 years of age or older, at the time of informed consent and body weight ≥40 kg. Adolescent subjects below the age of 18 years old (or country-specific age of majority) will only be enrolled in this study if instructed by the sponsor and approved by the country or regulatory/health authority. If these approvals have not been granted, only subjects aged 18 years (or country-specific age of majority) and older will be enrolled.

3. Meet all the following atopic dermatitis criteria:
 - Clinical diagnosis of chronic atopic dermatitis (also known as atopic eczema) for at least 1 year prior to Day 1 and has confirmed atopic dermatitis (Hanifin and Rajka criteria of AD; refer to (Appendix 2) at the Screening and Baseline visits;
 - Documented recent history (within 6 months before the screening visit) of inadequate response to treatment with topical medications for at least 4 weeks, or for whom topical treatments are otherwise medically inadvisable (eg, because of important side effects or safety risks), or who have required systemic therapies for control of their disease;
 - Moderate to severe AD (affected BSA $\geq 10\%$, IGA ≥ 3 , EASI ≥ 16 , and Pruritus NRS ≥ 4 at the baseline visit).
4. Willing and able to comply with scheduled visits, treatment plan, laboratory tests and other study procedures.
5. Female subjects who are of child-bearing potential (which includes all female subjects aged 12 years and older, regardless of whether they have experienced menarche) must not be intending to become pregnant, currently pregnant, or lactating. The following conditions apply:
 - a. Female subjects of childbearing potential must have a confirmed negative pregnancy test prior to randomization;
 - b. Female subjects of childbearing potential must agree to use a highly effective method of contraception (as per [Section 4.4.1](#)) for the duration of the active treatment period and for at least 28 days after the last dose of investigational product.

For Czech Republic only, 5 b. is revised and 5 c. is added to require:

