7.7.1. Pruritus Numerical Rating Scale (NRS)

Severity of Pruritus

The severity of itch (pruritus) due to atopic dermatitis will be assessed using the Pruritus Numerical Rating Scale, a validated horizontal NRS (Appendix 6).⁴² Subjects will be asked to assess their worst itching due to atopic dermatitis over the past 24 hours on an NRS anchored by the terms “no itch” (0) and “worst itch imaginable” (10). This item will be administered to all subjects. Subjects will enter the pruritus NRS assessment into an eDiary.

Frequency of Pruritus

The frequency of itch (pruritus) due to atopic dermatitis will be assessed using a horizontal NRS (Appendix 6). Subjects will be asked to assess frequency of itching due to atopic dermatitis over the past 24 hours on an NRS anchored by the terms “never/no itching” (0) and “always/constant itching” (10). This item will be administered to all subjects. Subjects will enter the pruritus NRS assessment into an eDiary.

The Pruritus NRS should be completed as per [Schedule of Activities](#).

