This imputation will be repeated multiple times with different MCMC samples to obtain multiple completed datasets. For each such completed dataset, the estimates of the proportions and CMH-weighted difference of proportions between each PF-04965842 dose group and placebo will be obtained along with the associated standard errors using the methods in [Section 5.2.1](#). Rubin’s rule (Rubin, 1987) will be used to combine the multiple estimates and standard errors across the imputed datasets and provide p-values.

The above analysis can be repeated for different combinations of MNAR quantities which will be applied to the probability of response to assess when the conclusion might change (i.e., tipping). Two important scenarios are included in the tipping point analysis framework. When the MNAR quantities are zero and the posterior predictive probabilities in the PF-04965842 dose groups are not shifted, results are obtained under an assumption of MAR for the missing data mechanism. Alternatively, at the other extreme, when the MNAR quantities are 1.0 for each PF-04965842 dose group, results are obtained under an assumption that the distribution of the missing responses after discontinuation of either dose of PF-04965842 is the same as that of the missing responses on the placebo arm. More detailed descriptions are provided in [Appendix 3](#).

Due to a technical error in the process of transmission and collection of electronic data with the device, the data on the pruritus NRS scale was not collected from several subjects at the scheduled visits of Week 2 (Day 15) and after. This was not restricted to a particular site or country and was not indicative of being related to the missing value of pruritus endpoint or any other endpoints. As such, the missing data mechanism may be reasonably assumed to be missing completely at random or missing at random.

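### The eDiary is the only stated route for the pruritus NRS, so at Weeks 4 and 12, with one scheduled entry each, a device failure at the visit can lose a key secondary score

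*Protocol*

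**What the plan says.** **Endpoint.** Protocol Section 2 lists as key secondary a response of at least 4 points "improvement in the severity of pruritus numerical rating scale (NRS) from baseline at Weeks 2, 4, and 12". Protocol 9.2.2 and SAP 5.1 place the key secondary tests inside the procedure that controls the familywise error at 5%.

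**Mode of entry.** Protocol 7.7.1: "Subjects will enter the pruritus NRS assessment into an eDiary". The NRS is recorded daily in screening and from Day 1 to Day 15. Schedule of Activities, footnote q, then says: "After Day 15, the pruritus NRS will be completed only on study visit days in the eDiary". Section 6.2.3 gives the same instruction at the Week 2 visit.

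**Device failure.** Protocol 7.7: "In the event of electronic malfunction, a replacement device will be shipped to the site". The same section mentions paper versions of the instruments as appendix examples. It does not name them as a back-up.

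**Subjects who cannot use the device.** Protocol 7.7 says that, where the difficulty is documented, "the subject will be permitted to enter or remain in the study". It does not say how their NRS is then obtained. Inclusion criterion 3 (Protocol 4.1) requires a pruritus NRS of at least 4 "at the baseline visit", and SAP 4.1 and 6.3.1 limit the NRS4 analysis to subjects with a baseline of at least 4.

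**What happened.** SAP 5.3.1 attributes a loss of scores to a technical error in transmitting and collecting entries from the handheld: "the data on the pruritus NRS scale was not collected from several subjects at the scheduled visits of Week 2". Later visits were hit as well. The SAP version history adds that several sites were affected.

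**The concern.** A visit-day NRS score has a 24-hour recall, so a replacement device that arrives later cannot reproduce it. From Day 16 there are no home entries to fall back on. If the device fails at Week 4 or Week 12, following the stated rule leaves a gap in a key secondary endpoint although the subject is in the clinic and could answer one question on paper.

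The second gap is one of consistency. Section 7.7 admits subjects who cannot use the device, while eligibility and the NRS4 population both need a baseline score, and no route for recording that score is given.

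Non-dropout gaps in NRS4 are either imputed by a model or left missing. In Sequence A testing stops at the first hypothesis not rejected, so a failed itch test there also closes whatever follows it. The order within Sequence A is in a figure that was not available for this check.

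**Working it through.** **1. Which visits are exposed.** Entry rules: Schedule of Activities, footnote q, and Protocol 6.2.3. Analysis windows: SAP Appendix 2, which keeps the value closest to the target day. Baseline rule: SAP 3.4.

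| Time point | Window | Scheduled NRS entries in window | If the device fails on the visit day |
|---|---|---|---|
| Baseline | Day 1, else last earlier value | daily in screening | earlier diary value is used |
| Week 2 | Days 2–22 | up to 15 − 2 + 1 = 14 (Days 2–15) | Day 14 entry can stand in |
| Week 4 | Days 23–43 | 1 | no other scheduled entry |
| Week 12 | Days 72–99 | 1 | no other scheduled entry |

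The Week 6 contact on Day 43 is a telephone call, and Section 6.2.5 lists only PSAAD for it. The exposure is therefore at Weeks 4 and 12. For a subject who never uses the device, all rows are exposed.

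**2. What the analysis does with a gap.** Under SAP 5.3.1 and 6.3.1, dropouts count as non-response and other gaps are multiply imputed under MAR. If 5 or fewer subjects are missing in each arm at a visit, the gaps stay missing; on placebo that is up to 5/75 = 6.7% of the arm. A sensitivity analysis in the FAS counts all missing values as non-response.

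**3. Check of the power method.** The documents give no power for NRS4, so the method was first tested on the stated co-primary figures (Protocol 9.1). With n₁ = 75, n₂ = 150 and p̄ the pooled rate:

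power = Φ{[|p₂ − p₁| − z·√(p̄(1 − p̄)(1/n₁ + 1/n₂))] / √(p₁(1 − p₁)/n₁ + p₂(1 − p₂)/n₂)}

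- IGA, 6% vs 26%, z = 1.96: p̄ = (4.5 + 39)/225 = 0.1933; (0.20 − 0.1095)/0.0451 = 2.007; power 97.8%. The stated figure of at least 95% holds.
- EASI-75, 15% vs 45%: power 99.8%. The stated figure of at least 99% holds.
- Both: 0.95 × 0.99 = 94.05%, in line with the stated 94%.

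**4. Illustration for NRS4.** Response rates and loss fraction m are assumptions, with m equal in the arms. In each cell the first figure leaves lost values missing (n × (1 − m)). The second counts them as non-response (both rates × (1 − m)). Both test levels are shown because Sequence A runs at 5% or 2.5% depending on the Week 2 result.

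| Assumed rates, level | m = 0 | 5% | 10% | 20% | 30% |
|---|---|---|---|---|---|
| 15% vs 35%, 2.5% | 84.3 | 82.1 / 81.2 | 79.6 / 77.8 | 73.7 / 69.9 | 66.7 / 60.8 |
| 15% vs 35%, 5% | 90.7 | 89.2 / 88.5 | 87.4 / 86.0 | 82.9 / 79.9 | 77.3 / 72.3 |
| 15% vs 45%, 2.5% | 99.5 | 99.3 / 99.1 | 98.9 / 98.5 | 97.9 / 96.4 | 95.8 / 92.2 |

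To give m a scale: if 8 or 15 placebo scores were lost, that would be 8/75 = 10.7% or 15/75 = 20.0%. These counts are assumed. The table concerns total loss; the part that a paper form could prevent is only the part visible at the visit, and its share is unknown.

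**The case against.** The strongest reply has five parts.

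- **Most of the itch data are protected.** This stands for Week 2 and for the analysis baseline. A reader might infer that any clinic-day failure loses a key secondary score; SAP 3.4 and Appendix 2 show otherwise. At Weeks 4 and 12 the wide windows would also accept a score from another day, but neither document asks for one.
- **The SAP event is a different failure.** A reader might infer that it is the failure described in Section 7.7 and that paper would have saved every score. The documents do not support that. They describe an error in transmission and collection, and do not say whether anyone could see it at the visit. If entries looked complete, a rule triggered by an unusable device would not have fired.
- **Other modes are not forbidden.** This stands. That the eDiary is the only route is inferred from silence. Section 7.7 allows that an electronic device may not always be used, and a site or vendor manual may hold a back-up. So the documents do not show that subjects unable to use the device necessarily have no score, nor do they waive the entry threshold. They leave the mode unstated.
- **The SAP already has a safeguard.** The non-response analysis does not rely on MAR, and observed scores are kept, so the result does not rest on imputation alone. But that analysis tests sensitivity to the gap without recovering the score.
- **Paper and electronic scores may differ.** Section 7.7 says that format or wording can vary slightly. This is a real cost, which recording the mode and a sensitivity run can address.

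**Conclusion.** The point holds in a limited form. The only stated malfunction rule can lose an NRS score at Week 4 or Week 12 that could have been collected on the spot. The route for subjects who cannot use the device is unstated, and Section 7.7 needs to be reconciled with inclusion criterion 3 and the NRS4 population.

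The size cannot be fixed, because neither document gives the number of lost scores or expected NRS4 rates. On the assumed rates above, a 20% loss costs about 11 to 14 points of power with a moderate effect at the 2.5% level (84.3 − 73.7 = 10.6; 84.3 − 69.9 = 14.4). With a large effect it costs 2 to 3 points (99.5 − 97.9 = 1.6; 99.5 − 96.4 = 3.1). If failures seen on site are few, the effect is small.

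The SAP's report shows that collection through the device process failed in this trial. It does not measure how much a paper back-up would have prevented. The stated co-primary power is not in question. The change is worth making because it is cheap.

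**What to change.** **Protocol 7.7 and 7.7.1.** State that at scheduled site visits, including baseline, the Appendix 6 paper NRS is completed if the device cannot be used or the subject has a documented inability to use it. It is done before other procedures and dosing, and entered on the CRF with the mode recorded. This fits the existing routine: Section 7.7 already has staff check PRO completeness before the visit proceeds, and Sections 6.2.4 and 6.2.7 have them review the visit's NRS entry. Taking it at baseline also lets inclusion criterion 3 be documented.

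**SAP 5.3.1 and 6.3.1.** Treat these scores as observed values. Add a sensitivity analysis of NRS4 without them, alongside the existing analysis that counts all missing values as non-response.

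**Cost.** A short protocol addition, one CRF field and one sensitivity run, with no added visit. The downside is a small number of mixed-mode scores. Two limits remain: the change does not help with faults that nobody sees at the visit, and it does not supply the daily home entries used for time to NRS4.

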7.7.1. Pruritus Numerical Rating Scale (NRS)

Severity of Pruritus

The severity of itch (pruritus) due to atopic dermatitis will be assessed using the Pruritus Numerical Rating Scale, a validated horizontal NRS (Appendix 6).⁴² Subjects will be asked to assess their worst itching due to atopic dermatitis over the past 24 hours on an NRS anchored by the terms “no itch” (0) and “worst itch imaginable” (10). This item will be administered to all subjects. Subjects will enter the pruritus NRS assessment into an eDiary.

Frequency of Pruritus

The frequency of itch (pruritus) due to atopic dermatitis will be assessed using a horizontal NRS (Appendix 6). Subjects will be asked to assess frequency of itching due to atopic dermatitis over the past 24 hours on an NRS anchored by the terms “never/no itching” (0) and “always/constant itching” (10). This item will be administered to all subjects. Subjects will enter the pruritus NRS assessment into an eDiary.

The Pruritus NRS should be completed as per [Schedule of Activities](#).

7.7.2. Patient Global Assessment (PtGA)

The PtGA asks the subject to evaluate the overall cutaneous disease at that point in time on a single-item, 5-point scale (Appendix 7). The same category labels used in the Investigator’s Global Assessment will be used for the Patient Global Assessment, ie, “severe (4)”, “moderate (3)”, “mild (2)”, “almost clear (1)”, and “clear (0)”. The PtGA should be completed as per [Schedule of Activities](#). This single-item scale will be administered to all subjects.

7.7.3. EuroQol Quality of Life 5-Dimension 5-Level Scale (EQ-5D-5L) and EuroQol Quality of Life 5-Dimension Youth Scale (EQ-5D-Y)

The EQ-5D is a validated, standardized, generic instrument that is the most widely used preference-based health-related quality of life questionnaire in cost-effectiveness and health technologies assessment (HTA) (Appendix 8).¹⁷⁻²⁰ Recently, a version was developed called EQ-5D-5L with 5 response levels on each dimension compared to the 3 response levels in the EQ-5D-3L.^{17,19,21,23} A version of the instrument specifically developed and validated for use by youths age 12 through 17 years is called the EQ-5D-Y.^{24,25,26}

Measurement properties of the EQ-5D-5L demonstrated to be a valid version of the 3-level questionnaire that improved measurements by adding discriminatory power, reducing the ceiling, and establishing convergent and known-groups validity.^{19,18,21,23} Both the EuroQol EQ-5D-3L and EQ-5D-5L versions are well-established instruments used to measure health

states and utilities in various diseases areas and assess mobility, self-care, usual activities, pain/discomfort, anxiety/depression and health status using a visual analog scale (VAS).^{20,26} The EQ-5D-3L was used previously in AD studies, including the dupilumab trials, to measure utilities.²⁷⁻³⁰

7.7.4. Dermatology Life Quality Index (DLQI) and Children's Dermatology Life Quality Index (CDLQI)

The DLQI is a validated general dermatology questionnaire that consists of 10 items to assess subject-reported health-related quality of life (daily activities, personal relationships, symptoms and feelings, leisure, work and school, and treatment) (Appendix 9).³¹ It has been extensively used in clinical trials for AD. The DLQI is a psychometrically valid and reliable instrument that has been translated into several languages, and the DLQI total scores have been shown to be responsive to change. The minimally important difference for the DLQI has been estimated as a 3 to 5 point change from baseline. A version of the instrument specifically developed and validated for use by adolescents from age 12 to 17 is called the CLDQI.³² The DLQI should be completed as per [Schedule of Activities](#).

